## **Objective**

Androgenetic alopecia (AGA) is a progressive condition with limited optimal therapeutic options. While platelet-rich plasma (PRP) therapy has been explored, the apheresis technique offers a distinct method of PRP preparation that yields higher platelet purity and more consistent cellular composition compared to conventional centrifugation methods. This study is specifically designed to evaluate the clinical effectiveness of this autologous apheresis PRP and identify key predictors.

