## **Design**

Given the exploratory nature of this investigation aimed at generating preliminary efficacy and safety data for a specific PRP preparation method, a single-arm design was chosen. This single-arm trial enrolled 201 male AGA patients receiving 3-5 sessions of autologous apheresis PRP injections. The primary endpoint, change in the BASP classification, was assessed by independent, blinded physicians. Patient-reported outcomes were assessed one month after treatment completion using a four-item questionnaire covering hair quality, hair thickness, hair loss reduction, and overall satisfaction. Associations between treatment response and key variables, including age, number of sessions, baseline severity, and PRP cellular composition were analyzed.

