### **Statistical Analysis**

Statistical analysis was performed using SPSS 26.0 and Prism 9.0 software. Continuous variables were tested for normality (Shapiro-Wilk test) and were presented as mean  $\pm$  SD or median (IQR), as appropriate. Categorical variables were expressed as n (%). Binary Logistic Regression Analysis was used to analyze the relationship between the effectiveness of PRP injection treatments and age, treatment sessions, initial severity at diagnosis, and cellular components in PRP. A crosstabulation analysis was conducted to assess the association between treatment

sessions and clinical effectiveness. Chi-square test was used to analyze the impact of treatment sessions on effectiveness, and Mantel-Haenszel Chi-square test was used to assess for a linear trend. Receiver Operating Characteristic (ROC) curve analysis was conducted to assess the predictive utility of PRP RBC concentrations for treatment failure (defined as 'no improvement'). A two-sided p-value of  $< 0.05$  was considered as statistical significance.

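### Predictive utility is judged from one ROC curve for RBC alone, in the cohort where all PRP components are modelled, with no statement of why or when RBC was chosen

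*Protocol*

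**What the plan says.** The Objective section sets two aims: "evaluate the clinical effectiveness of this autologous apheresis PRP and identify key predictors". Its rationale for apheresis is the purity of the platelets and the consistency of the cell mix.

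The Design section describes one cohort ("This single-arm trial enrolled 201 male AGA patients") and treats cell composition as a whole as a candidate predictor: "Associations between treatment response and key variables, including age, number of sessions, baseline severity, and PRP cellular composition were analyzed". It also qualifies the study: "Given the exploratory nature of this investigation".

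The Statistical Analysis section enters age, treatment sessions, "initial severity at diagnosis, and cellular components in PRP" in a binary logistic regression for effectiveness. Near its end it adds an ROC analysis to "assess the predictive utility of PRP RBC concentrations for treatment failure", with failure defined as no improvement. Significance is two-sided at 0.05.

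RBC content of the PRP is named nowhere else in the protocol. Hemoglobin and hematocrit appear under Participants, but only as eligibility blood tests.

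**The concern.** Several cellular components are related to response in one cohort. One of them alone then gets an ROC curve, in the same cohort, against the mirror image of the same outcome. The protocol gives neither a reason for choosing RBC nor the point at which it was chosen.

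The order matters. An AUC for a marker named before the data were seen estimates what it claims to estimate. An AUC for the marker that happened to do best among several is partly a record of that luck, and its p-value ignores the competition. The text does not let a reader tell which case applies.

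A second weakness does not depend on the order. A curve for RBC alone describes discrimination by RBC alone. It says nothing about whether RBC improves on age, baseline severity and number of sessions, which the plan already models. It also gives no comparison with the platelet component, which is prominent in the study's rationale. Identifying predictors is a stated aim, so a conclusion that RBC content predicts failure could rest on this one curve.

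**Working it through.** The protocol states no AUC, cut-off or expected failure rate, so there is no figure of its own to reproduce. The check asks how large the optimism would be under each possible order of events.

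**Inputs.** From the protocol: N = 201, one cohort, two-sided 0.05, no adjustment for the number of components mentioned. Assumed, because not given: all 201 analysed; number of components k = 3, 5 or 7; 40 or 60 failures (80 in part of step 4); correlation between components 0 or 0.5.

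**Step 1. RBC and its direction fixed in advance.** Simulated mean AUCs were 0.549-0.551, 0.600, 0.649-0.650 and 0.699-0.700 for true values of 0.55, 0.60, 0.65 and 0.70. There is essentially no bias.

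**Step 2. All components useless: chance that at least one is nominally significant.** For independent components this is 1 − 0.95^k:

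- k = 3: 1 − 0.8574 = 14.3%
- k = 5: 1 − 0.7738 = 22.6%
- k = 7: 1 − 0.6983 = 30.2%

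At correlation 0.5, simulation gives about 12-13%, 18-19% and 23-24%.

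**Step 3. All components useless: AUC of the best one.** The null standard error of the AUC is √[(N+1)/(12·n₁·n₀)].

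- 40 failures: √[202/(12·40·161)] = 0.051, so significance needs an AUC of at least 0.5 + 1.96·0.051 = 0.600.
- 60 failures: √[202/(12·60·141)] = 0.045, so the threshold is about 0.587.

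Simulated mean AUC of the best marker (independent components), direction taken from the data:

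| Components | 60 failures | 40 failures |
|---|---|---|
| 1 | 0.54 | 0.54 |
| 3 | 0.56 | 0.57 |
| 5 | 0.57 | 0.58 |
| 7 | 0.58 | 0.59 |

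The first row shows that choosing the direction from the data already gives about 0.54. Choosing among markers adds about 0.02-0.05 to that. A useless marker carried forward because it was significant must lie above the threshold, and averages about 0.60-0.62.

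**Step 4. One real marker among five, kept only if it is best and significant** (40 and 80 failures):

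| True AUC | Mean AUC shown, 80 failures | Mean AUC shown, 40 failures |
|---|---|---|
| 0.55 | 0.605 | 0.628 |
| 0.60 | 0.623 | 0.640 |
| 0.65 | 0.654 | 0.664 |
| 0.70 | 0.700 | 0.702 |

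The inflation matters for weak markers and disappears for moderately good ones.

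**Step 5. Precision.** By the Hanley-McNeil standard error, an AUC of 0.65 has a 95% half-width of about 0.09 with 60 failures and 0.10 with 40. An AUC reported without its interval would look firmer than it is, whatever the order of selection.

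**The case against.** The strongest reply is that no selection is documented. A reader might infer that the regression was used as a screen and that RBC was its winner. The protocol does not say so: it describes a regression and, separately, an ROC curve for one named marker. A missing reason is not evidence of a data-driven choice. An interest in platelet purity is also compatible with an interest in contaminating red cells, although it does not explain why RBC alone was taken. This reply stands, so the optimism can only be stated conditionally.

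A reader might also infer that a cut-off for RBC will be read from the curve. None is planned in the text, so optimism in a cut-off is relevant only if one is derived.

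Validation details are commonly left to a statistical analysis plan, and one may exist. Their absence is therefore not the point. The point is that the protocol itself settles on one marker for a predictive statement, without a reason.

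Finally, the study calls itself exploratory, and the primary endpoint is change in BASP grade. That lowers the severity. It does not make a single-marker curve an adequate basis for a statement of predictive utility, nor does it answer the question of added value.

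**Conclusion.** The concern holds in conditional form and is minor. As written, the reader cannot tell whether the RBC curve is a test of a marker named in advance or the best result among several.

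In the first case the AUC is essentially unbiased. In the second the AUC is too high and the p-value too small. The false-positive rate is then about 12-24% (correlation 0.5) to 14-30% (independent) instead of 5%, with a mean AUC of about 0.56-0.59 for a best marker that is useless. The bias is small at a true AUC of 0.65 and negligible at about 0.70. The numbers of components and failures, and the correlation, are assumptions; the protocol gives none of them.

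The conclusion that RBC was in fact chosen from the regression results would go beyond the text. What holds under either order is that a single-marker curve cannot show that RBC adds to age, severity and sessions.

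**What to change.** 1. State why RBC was chosen, and whether it and its direction were fixed before the regression results were seen.
2. Report the AUC with a 95% CI for every cellular component entered in the regression, not only RBC.
3. Report the AUC of the model with age, baseline severity and sessions, with and without the cellular components.
4. Correct the model AUCs for optimism by bootstrap, repeating any marker selection inside each resample, and any cut-off as well if one is derived.
5. Base the statement on predictive utility on the corrected values. Unless RBC was fixed in advance, describe its single-marker result as hypothesis-generating.

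Cost: a few hours of analysis on data already collected. The downside is that the reported AUC will probably be slightly lower.

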### **Ethical considerations**

This study was approved by the Ethics Committee of the General Hospital of the Western Theater Command of the Chinese People's Liberation Army(2023xjsxxm-28). Written informed consent was obtained from all participants after a detailed explanation of the study procedures, potential risks, and benefits. Participant confidentiality would be strictly maintained by using coded identifiers for all data. The study adhered to the principles of the Declaration of Helsinki.
